### **Secondary outcome measures**

The secondary outcomes include change or differences in pleasantness ratings of deep pressure or intensity or pleasantness ratings of slow brushing and fast brushing before and after loss of A-beta and A-delta-associated sensory function (relative to unaffected arm).

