## Précis:

**Objective:** The sensory basis of non-painful deep pressure sensation is not known. We recently found that innocuous pressure sensation is eliminated in rare sensory neuronopathy patients with a specific loss of A-beta fibers, strongly suggesting that A-beta fibers underlie the ability to sense deep pressure. In addition, we and others have shown that deep pressure touch (observed in hugs and massage) frequently conveys a sense of pleasantness. The current study aims to examine the role of A-beta fibers in the perception of deep pressure touch including both its intensity and the pleasant affect it often elicits. This study constitutes the second study of the K99 phase of a K99/R00 grant application awarded to [name] by NCCIH.

**Study Population:** Up to 24 healthy participants will be enrolled in the study with a goal of 12 completers. Participants will be invited based on previous screening and participation in our studies.

**Design:** Participants will undergo an ischemic-compression block. Sensory stimuli will be administered at frequent intervals to capture the loss of sensation related to A fibers as the block progresses. Before and after A-beta-associated sensations have been lost, the perception of deep pressure will be tested. Participants will rate the intensity and pleasantness of the pressure. Ratings of pain and discomfort will be collected throughout the study session.

**Outcome measures:** Primary outcome; Rating of intensity of deep pressure on the blocked arm before versus after loss of A-beta sensation, compared to ratings on the unblocked arm.

Secondary outcomes: 1) Rating of pleasantness of deep pressure on the blocked arm after loss of A-beta sensation, compared to ratings on the unblocked arm; 2) Ratings of intensity and pleasantness of gentle brushing on the blocked arm after loss of A-beta sensation, compared to ratings on the unblocked arm.

Precis posted online at [clinicaltrials.gov](https://clinicaltrials.gov): see Attachment 2

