### b. Secondary objectives:

**Hypothesis 1:** Participants will experience a significant decrease in the pleasantness of deep pressure after loss of A-beta-associated sensation due to ischemic-compression block.

**Hypothesis 2:** Participants will experience a significant decrease in the intensity *but not* pleasantness of gentle brushing after loss of A-beta-associated sensation due to ischemic-compression block.

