## **9. Outcome Measures**

### **Primary outcome measures**

The primary outcome is the change or difference score (pre to post) in intensity ratings of deep pressure measured before and after loss of A-beta-associated sensations on the affected arm versus the unaffected arm (e.g. compared between arms by a paired t-test at the group level).

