#### Behavioral Data

All behavioral data will be analyzed using SPSS or similar statistical package. A significance level of  $p < 0.05$  will be adopted for all analyses.

For the primary and secondary outcomes, we will use paired t-test or equivalent nonparametric test to evaluate the effect of the nerve block

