## Attachment 2: Precis for clinicaltrials.gov

### Précis:

**Objective:** Our sense of touch includes the intensity, pleasantness and unpleasantness of touch. We are investigating the sensory fibers that convey these various aspects of touch sensation. The current study will examine the role of unmyelinated sensory fibers in the perception of several types of touch to the arm.

**Study Population:** Up to 24 healthy participants will be enrolled in the study.

**Design:** Participants will receive baseline sensory testing including perception of hot and cold temperatures, vibration, pressure, and gentle brushing touch. Then, a tourniquet (blood pressure cuff) will be inflated to cut off blood flow to one arm. This will test the role of certain sensory fibers in several different touch sensations. Sensory testing will continue for a maximum of 1 hour. Then, the nerve block will be released. Ratings of mood, anxiety, pain, discomfort, intensity, and pleasantness/unpleasantness will be collected throughout the study session.

**Outcome measures:** We will compare subjective ratings (including intensity and unpleasantness/pleasantness) before and after the nerve block on the blocked and unblocked arm to determine the role of unmyelinated and myelinated sensory fibers in the perception of light touch and deep pressure.

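### Does the Précis wording leave it open whether the secondary outcomes are pre-to-post changes or post-loss ratings only?

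*Combined protocol and SAP*

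**What the plan says.** The Précis, under Outcome measures, gives the primary outcome a baseline term: "Rating of intensity of deep pressure on the blocked arm before versus after loss of A-beta sensation, compared to ratings on the unblocked arm". The first secondary outcome, in the same paragraph, has none: "Rating of pleasantness of deep pressure on the blocked arm after loss of A-beta sensation, compared to ratings on the unblocked arm". The second, on gentle brushing, follows the same pattern.

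Section 9 defines the primary outcome as "the change or difference score (pre to post) in intensity ratings of deep pressure measured before and after loss of A-beta-associated sensations", affected against unaffected arm, and offers a paired t-test between arms as an example. The secondary paragraph directly below speaks of change or differences and ends "pleasantness ratings of slow brushing and fast brushing before and after loss of A-beta and A-delta-associated sensory function (relative to unaffected arm".

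Section 10a, Behavioral Data, covers both sets in one sentence: "For the primary and secondary outcomes, we will use paired t-test or equivalent nonparametric test to evaluate the effect of the nerve block".

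Section 4d plans ratings of slow brushing and deep pressure on both arms at baseline and again once A-beta sensation is lost. It describes one brushing speed, about 3 cm per second. Ratings after a separate loss of A-delta function are described there as optional and dependent on that state being seen.

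**The concern.** The two wordings are not the same estimand. A post-loss comparison of arms counts any difference that already existed at baseline as an effect of the block; a comparison of changes subtracts it. Both arms are rated at both times, so both quantities can be computed for every completer, and they can disagree. Because Section 10a does not name the paired quantity, the choice appears open until the data are in. These outcomes carry Hypotheses 1 and 2 of Section 2b, and Hypothesis 2 predicts a fall in brushing intensity but none in brushing pleasantness, so a free choice could help in either direction.

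Two smaller points add to the impression of looseness. Section 9 lists fast brushing, for which the text describes no stimulus, and it mentions A-delta loss without saying that this state may not be reached.

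**Working it through.** **1. The plan's own figure.** Section 10b uses a 2-point drop and a change SD of 1.7, so d = 2/1.7 = 1.18 (stated as 1.17). A paired t-test at two-sided 0.05 with n = 12 (noncentral t, 11 df) has 95.7% power at d = 1.17, so 12 reproduces; 12/(1 − 0.5) = 24 enrolled. This concerns the primary outcome, which has a baseline term in both places. No secondary outcome is powered.

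**2. How the two versions relate.** Let D_pre and D_post be the blocked-minus-unblocked differences at baseline and after loss.
- Précis wording: test the mean of D_post.
- Section 9 wording: test the mean of D_post − D_pre.

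They have the same expectation when the mean of D_pre is zero.

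**3. Which version the documents support.**
- Section 2b: "Participants will experience a significant decrease in the pleasantness of deep pressure after loss of A-beta-associated sensation due to ischemic-compression block". A decrease needs a starting value.
- Précis, Design: "Before and after A-beta-associated sensations have been lost, the perception of deep pressure will be tested".
- Section 4d: baseline and post-loss ratings on both arms.
- Section 9: change for the primary, and change or differences before and after loss for the secondaries.
- Attachment 2: "We will compare subjective ratings (including intensity and unpleasantness/pleasantness) before and after the nerve block on the blocked and unblocked arm".

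Only the Précis outcome sentence stands apart.

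**4. Cost of choosing after the fact (illustrative).** The documents give no SD for pleasantness or brushing and no between-arm correlation, so these inputs are assumptions: SD 1.7 borrowed from Section 10b, between-arm error correlation ρ of 0 or 0.5, and SD s of stable arm differences of 0, 0.85 or 1.7.
- Error SD per rating: e = 1.7/√2 = 1.20.
- Between-arm error SD: d = e√(2(1 − ρ)) = 1.70 or 1.20.
- SD of post-only: √(d² + s²), from 1.20 to 2.40.
- SD of change: d√2 = 2.40 or 1.70.

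With no block effect and no mean arm difference, simulated trials in which either version gives p < 0.05 make up 8.5% to 9.4%, against 5% for one fixed version.

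**5. Baseline arm difference (illustrative).** With a fixed mean difference of 0.5 point and no block effect, post-only rejects in 10% to 26% of trials; at 1.0 point, 26% to 75%. Those rates require every participant's blocked arm to be shifted the same way on average. Section 4d tests half the participants on the dominant arm and half on the other. A dominance effect then enters with opposite signs and, split 6/6, cancels in the mean:

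| Dominance effect | SD 1.20 | SD 1.70 | SD 2.40 |
|---|---|---|---|
| 0.5 point | 3.5% | 4.1% | 4.6% |
| 1.0 point | 1.2% | 2.4% | 3.5% |

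The rates fall below 5% because the opposite shifts widen the spread without moving the mean. Completers may not split exactly 6/6. At 8/4 the residual mean shift is (8 − 4)/12 = 0.33 of the dominance effect, and the same simulation gives 5.1% to 5.7% over these six cells.

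**6. Precision.** Power for a 2-point drop with no mean arm difference:
- ρ = 0, s = 0: post-only 2/1.70 = 1.18, 96%; change 2/2.40 = 0.83, 75%.
- ρ = 0.5, s = 1.7: post-only SD √(1.20² + 1.7²) = 2.08, 86%; change 2/1.70 = 1.18, 96%.

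Neither version is more precise throughout.

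**The case for a change.** The strongest case for acting is that the baseline term is present for the primary and absent for the secondaries within one paragraph, which could be read as deliberate, and that the analysis section does not settle it. Section 9's phrase covering change or differences is itself loose, and its paired t-test is given as an example for the primary only. Naming the quantity would cost one sentence. Balancing dominance also does not rule out every source of a baseline arm difference.

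Most of this is fair as description. The Précis sentence does differ, and Section 10a does not name the paired quantity. But a summary does not override the section that defines the outcomes. Section 10a applies one test to primary and secondary outcomes together, so the form given for the primary carries over naturally. An analyst who follows Section 9 uses the version that is protected against a baseline arm difference. The inflation figures need either selection by result, which nothing in the documents suggests, or a systematic offset that no document identifies. Selection of a significant version would also work against the predicted absence of a fall in brushing pleasantness.

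One caution stands. Where change is the less precise version, a non-significant result for brushing pleasantness is easier to obtain. That bears on interpretation, since non-significance under either version is weak evidence of no decrease.

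**Conclusion.** No change follows. The operative text already gives pre-to-post change relative to the other arm, and the hypotheses, the schedule of ratings and Attachment 2 agree with it. What remains is a shortened summary sentence and an unnamed quantity that analysts would fill from Section 9. Treated as a real choice, change against post-only is a trade-off: 75% against 96% power in the least favourable illustrative cell, and 96% against 86% in the opposite one.

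Fast brushing is a stray term on the text available; Figure 1 is not shown and might mention it. The condition on A-delta ratings is already in Section 4d.

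This rests on three things: Section 9 takes precedence over the Précis, arm dominance is balanced roughly as planned, and the SD of 1.7 and the correlations serve as illustration only, because the documents give no variability for these outcomes. The primary outcome, the data collected and the 12 completers are untouched.

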## 10. Statistical Analysis

### a. Analysis of data/ study outcomes

#### Testing for normal distribution

All data will be assessed for normality of distribution using the Shapiro Wilk W test. A significant W statistic indicates that the hypothesis of a normal distribution should be rejected, i.e. a significant W indicates skewed data. If the data is skewed the data transformation method will be chosen based on the distribution (Box-Cox method) of the dependent variable. The resulting transformed data will be analyzed with parametric statistics. In the descriptions below we will describe the parametric statistical tests. If data transformation does not work, non-parametric tests will be applied.

#### Behavioral Data

All behavioral data will be analyzed using SPSS or similar statistical package. A significance level of  $p < 0.05$  will be adopted for all analyses.

For the primary and secondary outcomes, we will use paired t-test or equivalent nonparametric test to evaluate the effect of the nerve block

### b. Power analysis

In order to yield meaningful statistical analyses of the psychophysical data, and specifically for our primary outcome measure, we estimate that the sample size required to complete the study would be 12 healthy participants. G\*Power (<http://www.gpower.hhu.de>) was used to compute the necessary sample size. In our recent study of deep pressure perception (manuscript in preparation; data available upon request), the same oscillating deep pressure sequence was rated as an intensity  $M = 4.2$  (scaled to our 0-10 scale); we expect intensity to drop at least 2 points on our 0-10 rating scale (likely more since patients lacking A-beta fibers had no perception of deep pressure in our previous study, Case & [name] et. al., under review). In our previous study healthy participants rated the same deep pressure sequence on two different days and the standard deviation of the change in their rating from Day 1 to Day 2 was 1.7. Based on a

2-point change (due to blocking A-beta fibers which should fully eliminate sensation) and a standard deviation for within-subject rating change scores of 1.7, we expect a Cohen's effect size  $d = 1.17$ . Setting statistical power to 95% and Type I error probability to  $\alpha=0.05$ , 12 subjects would be required to complete the study. We expect up to a 50% dropout rate of participants based on prior NIH studies and the discomfort of prolonged nerve blocks found in other studies [13]. Thus, we will enroll up to 24 participants and dropouts will be replaced.

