## 2. Study Objectives

### a. Primary objective:

**Hypothesis:** Participants will experience a significant decrease in the intensity of deep pressure after loss of A-beta-associated sensation due to ischemic-compression block.

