#### d. Study procedures

Participants eligible to proceed will be asked to complete a single session, in the NIH Clinical Research Center.

An LHP will review eligibility criteria at the beginning of each session, to confirm that participants remain eligible and meet day-of-study criteria (5-10 minutes). Then, the nerve block procedure and sensory testing will be performed as depicted in **Figure 1. Study Flow** and described in detail below (approximately 1 hour, all procedures for research purposes):

[figure not shown]

Figure 1. Study Flow

Each nerve block session will follow approximately the timeline shown. Timing is approximate as nerve blocks progress at different speeds for different individuals.

Baseline affective touch testing will be performed on both arms (ratings of the intensity and pleasantness of slow brushing and deep pressure). The tourniquet will be placed by a LHP. Sensory testing will be conducted regularly to monitor block progression and loss of A-beta-associated sensation. When A-beta associated perception has been substantively eliminated, ratings of slow brushing and deep pressure (affective touch) will be repeated on each arm/hand. Sensory monitoring will continue and affective ratings may be repeated if further A-beta or A-delta percepts are lost before C-fiber function (loss of warm perception; this separation is not always observed; [14]). Testing is likely to be completed within 30-40 minutes from block placement. The nerve block will be removed by 60 minutes from placement.

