### **Details of Sensory testing paradigm**

Ratings of intensity and pleasantness of pressure and brushing: At baseline and after loss of sensation associated with A fibers, perception of deep pressure and gentle brushing will be tested on both arms. Deep pressure will be administered to the hand and wrist for approximately 20 seconds using a hand massager that applies oscillating pressure. Gentle brushing will be administered to the hand/forearm by a trained experimenter at a rate of approximately 3cm/second for approximately 15 seconds. Participants will rate intensity and pleasantness of each sensation on VAS scales with anchors of “no sensation” to “highest possible intensity” and from “extremely unpleasant” to “neutral” (midpoint) to “extremely pleasant.” Nearly identical VAS scales have been successfully used in our lab in numerous previous studies to distinguish the intensity versus pleasantness of sensory stimuli (e.g. [16, 17]). If cool perception is lost after light touch (not concurrently), A-delta fibers may be isolated and ratings can be collected again. Loss of cool and light touch often coincide, however [14]. Ratings of bad mood and anxiety will also be collected. They will be rated verbally on 0-10 scales (0 = none; 10 = worst you have experienced).

After placement of the tourniquet but before elimination of A-beta associated sensation, sensory testing will be conducted to monitor the block progression. Sensory testing will be conducted nearly continuously, which each test conducted approximately every ~1-2 minutes. All testing will be conducted distal to the block. The tests conducted during sensory monitoring may include the following:

Vibration perception (A-beta): A custom vibration device administering ~200 Hz vibration to the skin of the palm will be set for a random duration between 1-6 seconds. Participants will press a button (or similar response) when they perceive the onset and offset of the vibration.

Warm (C-fiber) and cool (A-delta) perception: Heat stimuli will be administered by the trained experimenter to the ventral surface of the forearm or palm using a contact

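### The 95% power in Section 10b is calculated for a single change score, whereas the primary test compares two change scores; the SD that test needs is not stated and, for a 2-point difference tested two-sided, can be at most about 1.74

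*Combined protocol and SAP*

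**What the plan says.** Section 10b (Power analysis) says that its sample size is "specifically for our primary outcome measure". The inputs are a mean effect, "we expect intensity to drop at least 2 points on our 0-10 rating scale", and a spread from an earlier study in which healthy participants rated the same pressure sequence on two days: "the standard deviation of the change in their rating from Day 1 to Day 2 was 1.7". These give d = 1.17 and, with power 95% and alpha 0.05, 12 completers. An expected dropout of up to 50% then leads to the enrolment ceiling of 24.

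Section 9 (Primary outcome measures) defines the outcome as the pre-to-post change in deep-pressure intensity "on the affected arm versus the unaffected arm (e.g. compared between arms by a paired t-test at the group level"). The Précis gives the same contrast: intensity "on the blocked arm before versus after loss of A-beta sensation, compared to ratings on the unblocked arm". Section 4d (Details of Sensory testing paradigm) collects the data for it: at baseline and again after the loss of sensation, "perception of deep pressure and gentle brushing will be tested on both arms".

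The test's sidedness is not stated. The hypothesis in Section 2a is directional: "Participants will experience a significant decrease in the intensity of deep pressure after loss of A-beta-associated sensation".

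**The concern.** The primary analysis is a paired t-test on two change scores per person, one from each arm. Its standard error depends on the SD of the within-person difference between those two changes. Section 10b supplies the SD of one change, from a setting in which no between-arm contrast or nerve block is described. The two SDs coincide only under conditions the plan does not mention.

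The 95% is the only quantitative reason given for 12 completers, and through the dropout allowance it also sets the ceiling of 24. A reader of Section 10b would take it as the power of the primary test and could not see that it depends on an unstated SD. The validity of the test is not at stake: the paired t-test holds its type I error whatever the between-arm correlation. Only the power statement is affected.

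**Working it through.** **Inputs from the plan.** Difference 2 points, SD of one change 1.7, d = 1.17, alpha 0.05, power 95%, n = 12 (all Section 10b); paired t-test on the two arms' changes (Section 9).

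**Not in the plan.** Sidedness, the SD of the between-arm difference in change, and the between-arm correlation ρ of the changes.

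**Method.** Paired t-test with the exact noncentral t distribution: df = n − 1, noncentrality = d × √n.

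**1. The plan's own figure.** d = 2/1.7 = 1.176, which the plan gives as 1.17. At d = 1.17:

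- Two-sided 0.05: n = 11 gives 0.937 and n = 12 gives 0.957, so 12 are needed.
- One-sided 0.05: n = 9 gives 0.939 and n = 10 gives 0.961, so 10 would be enough.

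The plan's 12 is thus reproduced by a two-sided test. That is how two-sidedness is inferred here.

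**2. What the primary test needs.** Let D be the blocked-arm change minus the unblocked-arm change. Then Var(D) = s_B² + s_U² − 2ρ·s_B·s_U. With n = 12 and two-sided 0.05, 95% power requires d of at least 1.146. For a 2-point net difference, SD(D) can be at most 2/1.146 = 1.745. Power is 0.951 at SD 1.74 and 0.949 at SD 1.75. This limit needs no assumption about either arm separately.

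**3. If each arm's change has SD 1.7 (assumption).** SD(D) = 1.7 × √(2(1 − ρ)). Setting this to 1.745 gives ρ = 1 − (1.745/1.7)²/2 = 0.473. With n = 12, two-sided 0.05:

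| ρ | SD(D) | Power, 2 points | Power, 3 points | Difference giving 95% |
|---|---|---|---|---|
| 0 | 2.404 | 0.747 | 0.975 | 2.76 |
| 0.25 | 2.082 | 0.857 | 0.995 | 2.39 |
| 0.4 | 1.862 | 0.922 | 0.999 | 2.13 |
| 0.5 | 1.700 | 0.959 | 0.9998 | 1.95 |
| 0.6 | 1.521 | 0.985 | above 0.9999 | 1.74 |

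A simulation of the paired t-test on change scores (200,000 runs) gave 0.746, 0.858, 0.922, 0.960 and 0.985 for the 2-point column, with type I error 0.050 throughout.

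**4. Other assumptions, 2 points, n = 12, two-sided.**

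- Smaller SD in both arms, ρ = 0: 1.4 per arm gives 0.889; 1.2 per arm gives 0.960.
- Unequal SDs, 1.7 in one arm and 1.0 in the other: 0.891, 0.950 and 0.977 at ρ = 0, 0.25 and 0.4.

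**5. If the test were one-sided.** The SD limit rises to 1.97. With 1.7 per arm this corresponds to ρ of about 0.33.

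**The case against.** The strongest reply is that nothing is miscalculated and that 12 is probably enough.

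- **The plan's 1.7 lies inside the limit of 1.74.** If the between-arm difference in change happens to have an SD of 1.7, the stated power is right. This is true, but with 1.7 in each arm it means a correlation of 0.5, and the plan states neither that correlation nor an SD for the difference.
- **Zero correlation with 1.7 per arm is an unfavourable corner.** The 1.7 is a between-day figure, whereas the trial takes all its ratings in one session: "Testing is likely to be completed within 30-40 minutes from block placement". Section 1 expects the painful context to act equally on both arms, and anything shared cancels in the contrast. A positive correlation or a smaller same-session SD is therefore plausible, and either could restore 95%. This stands as a reason to keep n = 12. It does not supply the missing value, and variability under a block could also be larger.
- **Two points is a stated minimum.** Section 10b expects a larger drop, from a mean of 4.2. With 1.7 per arm and ρ = 0, about 2.8 points gives 95%, and 4.2 points gives more than 99.9%. This also stands. But the 95% is quoted for 2 points. Moreover, the 2 points is the expected drop under the block; using it as the net difference assumes no mean change on the unblocked arm.
- **Sidedness is inferred.** The limit of 1.74 is for a two-sided test, and the sponsor should confirm the choice.

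**Conclusion.** The concern holds, as a minor point. Section 10b attributes 95% power to the primary outcome but calculates it for a single change score. For the test defined in Section 9, the figure depends on an SD that appears nowhere in the plan. With 12 completers, a 2-point net difference and a two-sided 0.05 test, that SD must be at most about 1.74. If each arm's change has SD 1.7, the limit corresponds to a correlation of about 0.47 or more, and power ranges from 75% at zero correlation to 98.5% at 0.6.

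The 95% is unsupported for the primary test; it is not shown to be false, and the trial is not shown to be underpowered. The conclusion rests on the outcome as defined in Section 9 and the Précis and on the plan's own 2-point difference. The range also rests on the per-arm SD of 1.7, which is an assumption of this check and not a statement of the plan.

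**What to change.** Keep 12 completers and the paired t-test on change scores. In Section 10b, confirm and state that the test is two-sided, state the assumed SD of the between-arm difference in change (or the per-arm SD and the correlation) with its source, and replace the flat 95%. Suggested text, if the sponsor confirms a two-sided test:

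> The primary test compares the blocked-arm change with the unblocked-arm change by a two-sided paired t-test at 0.05. With 12 completers, 95% power for a 2-point net difference requires an SD of the between-arm difference in change of at most 1.74. If each arm's change has SD 1.7, power is 75%, 86%, 92%, 96% and 98.5% at between-arm correlations of 0, 0.25, 0.4, 0.5 and 0.6, and at least 97% for a 3-point net difference at each of these.

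If the earlier study's data can support a smaller same-session SD or a between-arm correlation, give that value and the power that follows from it.

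The cost is two or three sentences. Sample size, primary test, procedures and data collection do not change. The drawback is that the stated power becomes a range whose lower end is less favourable than 95%.
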